5.7. Medical and Psychiatric History

Medical and psychiatric history events will be mapped to a Medical Dictionary for Regulatory Activities (MedDRA) version 23.1 or higher preferred term and system organ class. Medical and psychiatric history will be summarized by treatment group using preferred terms and system organ classes. All events will be listed.

5.8. Exposure to Treatment

The number of days on study drug, reasons for premature discontinuation of IMP, treatment compliance, days in each phase (Titration, Adjustment, and Maintenance), average dose in each phase, average L-Dopa dose during treatment period, and maximum tolerated dose will be summarized by treatment group for the FAS Population.

5.9. Primary Efficacy Analysis

5.9.1. Primary Estimand

The key research question for the primary endpoint will be addressed with an estimand based on the following attributes:

- 1) Treatments: treatments as randomized regardless of the actual treatment received.
- 2) Target study population of interest: subjects in the modified intent-to-treat (mITT) population.
- 3) Endpoint (variable) of interest: change baseline to Week 26 in total daily “on” time without troublesome dyskinesia based on the 2 day average of the self-completed home diary for motor function status (Hauser diary).
- 4) Population level summary of interest: estimated mean difference between tavapadon group and placebo group in the endpoint of interest.
- 5) Strategy for Intercurrent events (ICEs): a hypothetical strategy will be used to address intercurrent events (ICEs) of potential death, treatment discontinuations, missed visits/assessments, and start of prohibited concomitant Parkinson's disease medications.

The data after treatment discontinuations or after the start of prohibited Parkinson's disease concomitant medications (ATC classifications of ADAMANTANE DERIVATIVES, OTHER DOPAMINERGIC AGENTS, OTHER ANTIPARKINSON DRUGS, MONOAMINE OXIDASE B INHIBITORS, or ANTICHOLINESTERASES after the first dose of IMP and prior to the last dose of IMP with duration of 7 days or more) will be censored under the hypothetical strategy. The hypothetical strategy allows the study to assess the effect of tavapadon treatment without the confounding effect of prohibited concomitant Parkinson's disease treatments.

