9. COMT inhibitors, MAO-B inhibitors, amantadine, istradefylline, or anticholinergic drugs if use was initiated ≤90 days before the Baseline Visit	>14 days before Baseline Visit
10. Other investigational medications	>60 days before Screening Visit

Abbreviations: COMT = catechol-O-methyl transferase, CYP = cytochrome P450, ICF = informed consent, MAO = monoamine oxidase.

-- Not applicable. Any prior use is prohibited.

6.5.4 *Prohibited Medications During the Trial*

The concomitant medications that are prohibited during the trial are listed in [Table 7](#).

The medical monitor should be contacted regarding the appropriateness of a subject's continued participation in the trial in the event that initiation of therapy with a prohibited concomitant medication is deemed necessary, in the investigator's opinion, for the treatment of a treatment-emergent adverse event (TEAE).

Table 7 List of Medications Prohibited During the Trial

	Medication
1.	Sedatives, hypnotics, antidepressants, and anxiolytics (unless dose has been stable for >90 days before the Baseline Visit and will remain stable for the duration of the treatment phase) Note: Short-term use of lorazepam (up to 4 mg/day), or its equivalent, for TEAEs of anxiety or insomnia may be permitted following consultation with and approval by the medical monitor, but may not be taken within 12 hours prior to efficacy assessments during clinic visits. Use should be discontinued upon TEAE resolution.
2.	Atypical antipsychotics
3.	Dopamine antagonists, such as neuroleptics/antipsychotics (eg, phenothiazines, butyrophenones, thioxanthenes), including: 
 a. Haloperidol b. Trimethobenzamide or domperidone (for nausea/vomiting) c. Metoclopramide d. Quetiapine (for insomnia)
4.	COMT inhibitors, MAO-B inhibitors, amantadine, istradefylline, or anticholinergic drugs (unless use was initiated >90 days before the Baseline Visit and dose will remain stable for the duration of the treatment phase) Note: Short-term use of scopolamine for TEAEs of nausea may be permitted following consultation with and approval by the medical monitor, but may not be taken within 12 hours prior to efficacy assessments during clinic visits. Use should be discontinued upon TEAE resolution.
5.	Levodopa inhalation powder
6.	Dopamine agonists, including apomorphine
7.	Methyldopa
8.	Moderate or strong CYP3A4 inducers ^a (refer to Section 10.6 [Appendix 6] for examples)

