9.4 Statistical Analyses

Descriptive statistical methods will be used to summarize the data from this trial, with statistical testing performed for the efficacy endpoints. Unless stated otherwise, the term “descriptive statistics” refers to number of subjects (n), mean, median, standard deviation, minimum, and maximum for continuous data, and frequencies and percentages for categorical data. All available data for enrolled subjects will be listed by subject. Unless otherwise noted, the data will be sorted first by treatment group and subject number and then by date within each subject number.

All statistical analyses will be conducted with the SAS® System, version 9.4 or higher.

The remainder of this section is a summary of the planned statistical analyses of the primary and secondary endpoints as well as a description of planned safety analyses. Full details of these analyses will be included in the statistical analysis plan. The statistical analysis plan will be developed and finalized before database lock and will provide descriptions of the subject populations that will be used in the analysis and procedures for addressing missing, unused, and spurious data.

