9.4.1 Efficacy Analyses

The analysis of the primary and each secondary endpoint (Table 9) will include the comparison of tavapadon versus placebo. The hypothesis testing will be done in hierarchical order from the primary endpoint onward. To control for any potential inflation of Type I error that may be incurred from the interim analysis, the primary

hypothesis will be tested at an α level of 0.049 (2-sided) to ensure that the overall Type I error rate is below 0.05. Subsequent testing in the secondary endpoints will be conducted at an α level of 0.05 (2-sided).

Table 9 Efficacy Analysis

Endpoint	Statistical Analysis Methods
Primary and Key Secondary	
The primary endpoint (change from baseline to endpoint in “on” time without troublesome dyskinesia) and the key secondary endpoint (change from baseline to endpoint in “off” time) will be analyzed using an MMRM on the mITT population. This estimand will be based on the 2-day average of the self-completed Hauser diary from each postbaseline visit. A hypothetical strategy will be used to address the intercurrent events of discontinuation or use of prohibited medications with the data post intercurrent events treated as censored. The baseline value will be included as a covariate, and the treatment group (tavapadon or placebo), visit, and interaction between treatment group and visit will be included as fixed factors in the MMRM. The difference between tavapadon versus placebo at endpoint will be estimated based on the LSMeans from the MMRM. The key secondary endpoint will be analyzed in a similar manner.
 
Sensitivity analyses for the primary and secondary endpoints will be conducted with different assumptions on missing mechanism. Sensitivity analysis will also be conducted on the endpoint completer set with MMRM.

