5.9.3.3. Impact of Missing Values Handling

Whilst every effort will be made to prevent avoidable missing values during the study conduct ([National Research Council, 2010](#)), it is unrealistic to expect no missing values in clinical trials. The impact of missing values on the analysis results will be assessed by the sensitivity analyses described below.

Under Missing at Random (MAR) Assumption

Multiple imputation (MI) will be performed to replace each missing value with a set of plausible values that represent the uncertainty about the correct value to impute. The Markov chain (MCMC) method will be utilized for the mITT set. SAS PROC MI will be used to generate 27 possible imputed datasets: Each of these datasets will be analyzed using PROC MIXED in SAS using the MMRM model as described in [Section 5.9.2](#). The results of the analyses of the datasets will be combined using PROC MIANALYZE to produce an inferential result.

Considerations of Data Potentially Missing Not at Random (MNAR)

A pattern mixture model (PMM) approach will be used to address potentially MNAR patterns. The following three patterns of subjects in the mITT set will be considered:

- 1) Subjects with no missing values from discontinuation or from initiation of prohibited Parkinson's disease concomitant mediation during treatment period.
- 2) Subjects with missing values from the types of ICEs below will be considered having MNAR
 - a. Subjects who discontinue due to reasons, as recorded on the eCRF, of lack of efficacy, adverse events associated with motor symptoms of Parkinson's disease, physician decision, and withdrawal by subject.
 - b. Subjects who initiated concomitant Parkinson's disease medications (ATC classifications of ADAMANTANE DERIVATIVES, OTHER DOPAMINERGIC AGENTS, OTHER ANTIPARKINSON DRUGS, MONOAMINE OXIDASE B INHIBITORS, or ANTICHOLINESTERASES) after the first dose of IMP and prior to the last dose of IMP with a use duration of 7 days or more will be considered having a potential confounding ICE. The efficacy data post ICE will be treated as missing with the missing pattern of MNAR.

The MNAR cases will be identified and documented prior to database lock and unblinding ([Section 9.6](#)).

- 3) Subjects with missing values from the type of ICEs below will be considered as having MAR

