5.11. Summary of Primary and Key Secondary Efficacy Analyses

ICE Strategy	Primary Analysis	Sensitivity Analysis	Subgroup Analysis
Primary Endpoint: Change from Baseline to Week 26 in daily “on” time without troublesome dyskinesia based on the 2-day average of the self-completed home diary for motor function status (Hauser diary).			
Hypothetical strategy with data after treatment discontinuations or after the start of prohibited concomitant medications censored	
 ■ mITT population ■ Treatment as randomized ■ MMRM described in Section 5.9.2 	
 ■ Treatment effect at final dose levels ■ Treatment effect based on actual treatment received, if applicable ■ Missing values imputation using multiple imputations (MI) ■ Missing values imputation using pattern mixture model (PMM) ■ Endpoint completer analysis 	
 ■ Age ■ Sex ■ Hoehn&Yahr Status ■ Baseline daily “on” time without dyskinesia ■ Baseline daily “off” time ■ Race ■ Region
Key Secondary Endpoint: Change from Baseline to Week 26 in daily “off” time on the 2-day average of the self-completed home diary for motor function status (Hauser diary).			
Hypothetical strategy with data after treatment discontinuations or after the start of prohibited concomitant medications censored	
 ■ mITT population ■ Treatment as randomized ■ MMRM described in Section 5.9.2 	
 ■ Treatment effect at final dose levels ■ Treatment effect based on actual treatment received, if applicable ■ Missing values imputation using multiple imputations (MI) ■ Missing values imputation using pattern mixture model (PMM) ■ Endpoint completer analysis 	
 ■ Age ■ Sex ■ Hoehn&Yahr Status ■ Baseline daily “on” time without dyskinesia ■ Baseline daily “off” time ■ Race ■ Region

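### The drug-class list that triggers censoring in the primary estimand (SAP 5.9.1 and 5.9.3.3, pattern 2b) is not mapped to the prohibited antiparkinsonian drugs in protocol Table 7

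*SAP*

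**What the plan says.** **The rule.** SAP 5.9.1 applies a hypothetical strategy and censors data after treatment discontinuation or after the start of prohibited PD medication. It defines that medication as "ATC classifications of ADAMANTANE DERIVATIVES, OTHER DOPAMINERGIC AGENTS, OTHER ANTIPARKINSON DRUGS, MONOAMINE OXIDASE B INHIBITORS, or ANTICHOLINESTERASES after the first dose of IMP", with use of 7 days or more before the last dose. Its stated aim is: "The hypothetical strategy allows the study to assess the effect of tavapadon treatment without the confounding effect of prohibited concomitant" PD treatments.

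**The sensitivity analysis.** Pattern 2b in SAP 5.9.3.3 repeats the five labels and the time condition, "after the first dose of IMP and prior to the last dose of IMP with a use duration of 7 days or more". The same section adds: "The MNAR cases will be identified and documented prior to database lock and unblinding", with a reference to Section 9.6.

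**The prohibited drugs.** Protocol Table 7 (Section 6.5.4) covers antiparkinsonian drugs in items 4 to 6:

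- Item 4: COMT inhibitors, MAO-B inhibitors, amantadine, istradefylline and anticholinergics, with exceptions for stable prior use and for approved short-term scopolamine.
- Item 5: levodopa inhalation powder.
- Item 6: "Dopamine agonists, including apomorphine".

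**The same rule elsewhere.** Protocol Table 9 speaks of "discontinuation or use of prohibited medications with the data post intercurrent events treated as censored". SAP 5.11 has "Hypothetical strategy with data after treatment discontinuations or after the start of prohibited concomitant medications censored" for both endpoints. SAP 5.10.1 restates the rule for the key secondary endpoint. None of these three gives a class list or a minimum duration.

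**The concern.** An estimand that removes the influence of prohibited PD treatment needs a trigger that corresponds to what the protocol prohibits. Here the trigger is a list of class labels that cites no protocol table and differs from Table 7 in both directions.

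If a prohibited antiparkinsonian drug is not captured and the subject stays on study drug, later diary values remain in the primary analysis and can carry that drug's effect. If a listed drug is not prohibited, valid data can be censored. Because pattern 2b uses the same list, that sensitivity analysis would not reveal either problem.

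**Working it through.** **1. Compare the seven groups in Table 7 items 4 to 6 with the SAP labels.** Baseline status comes from inclusion criterion 10 and protocol Table 6.

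| Item | Group | Label that names it | Status at baseline |
|---|---|---|---|
| 4 | MAO-B inhibitors | MONOAMINE OXIDASE B INHIBITORS | allowed if long-standing and stable |
| 4 | Amantadine | ADAMANTANE DERIVATIVES | allowed, same condition |
| 4 | COMT inhibitors | none | allowed, same condition |
| 4 | Istradefylline | none | allowed, same condition |
| 4 | Anticholinergics | none | allowed, same condition |
| 5 | Inhaled levodopa | none | washed out |
| 6 | Dopamine agonists, apomorphine | none | washed out |

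The groups number 5 + 1 + 1 = 7. Two are named, so 7 − 2 = 5 are not. OTHER DOPAMINERGIC AGENTS and OTHER ANTIPARKINSON DRUGS may cover some or all of the five. On the documents alone the uncaptured number is 0 (widest reading) to 5 (names only).

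**2. Which groups matter most.** SAP 5.6 uses the identical five labels to describe PD drugs at baseline. A list built for that purpose would be meant to cover the three unnamed groups that are allowed at baseline, presumably through the OTHER labels. It would have no need to cover the two that must be washed out. That leaves agonists and inhaled levodopa. This is an inference, but the version 3.0 amendment log adds weight: it gives rescue therapies as the reason for listing inhaled levodopa and apomorphine as prohibited.

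**3. The reverse mismatch.** ANTICHOLINESTERASES has no counterpart in Table 7, which lists anticholinergics. In 5.9.1 the word prohibited precedes the list, so a reader could take the labels as a further restriction. Pattern 2b omits that word, so there the label acts on its own.

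**4. Cost of wider censoring.** Inputs are SAP Table 5 (270 completers, 135 per arm, SD 2.5, two-sided alpha 0.049) and a difference of 1 hour. Power is from the two-sample t-test, with noncentrality δ / (SD × √(2/n)).

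- As planned, n = 135: 1 / (2.5 × √(2/135)) = 3.29, power 90.4%. This reproduces Table 5.
- If 5% of completers were lost (assumed), 270 × 0.95 = 256.5, about 128 per arm: power 88.9%.

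**5. Courses shorter than 7 days.** The endpoint is Week 26 (SAP 4.1.3), target Day 182, and uses two diary days. A 6-day course touches a fixed pair of days on 6 + 1 = 7 possible start days. With a random start over 182 − 1 = 181 days, that is 7/181 = 3.9%, or about 4%.

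**6. Size of any bias.** The documents give no usage rates. As a conversion only, with every input assumed, an arm difference in uncaptured use of 1 to 5 percentage points times 0.5 to 2 hours gained gives 0.01 × 0.5 = 0.005 h to 0.05 × 2 = 0.10 h, against the planned 1 hour. An excess on placebo would dilute the effect, and an excess on tavapadon would overstate it. The upper end needs both maxima together, in subjects who stay on study drug.

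**The case against.** **Names are not capture.** A reader might infer that five of seven prohibited groups escape censoring. The documents do not support that. Class labels do not list their members, two of the five labels are catch-alls, and membership follows from the drug-dictionary coding, which is not shown. This objection stands, so the claim here is only that the written rule does not show that each item is captured.

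**The key secondary endpoint.** A reader might infer that it follows a different rule, because SAP 5.10.1 does not cite the 5.9.1 list. But 5.10.2 describes its analysis as similar to the primary one, and protocol Table 9 treats both endpoints together. What is missing is an explicit pointer.

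**The 7-day minimum.** A reader might see a contradiction with Table 9, 5.10.1 and 5.11. The protocol says "Full details of these analyses will be included in the statistical analysis plan", so the SAP may add a limit. Section 5.11 is a summary table and 5.10.1 reads as shorthand. SAP 5.15.4 uses a similar one-week threshold for levodopa dose changes. This is mainly a drafting difference.

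**Short courses.** Visits between Weeks 2 and 26 are 21 to 28 days apart, so a reader might compute that a 6-day course touches diary days in 7/28 to 7/21 of cases (25% to 33%). That is the chance for any visit; the Week 26 figure is about 4%.

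**Safeguards.** Protocol 7.3 lists both prohibited medication and worsening that needs added anti-PD medication as reasons for stopping study drug, and data after stopping are censored anyway. Concomitant drugs are tabulated by arm, and deviations are reviewed before lock. These limit leakage without closing the gap: 7.3 says that a subject may discontinue, and 6.5.4 provides for consulting the medical monitor about continued participation when a prohibited drug is needed to treat an adverse event.

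**Conclusion.** The point holds as a mismatch between the written censoring rule and protocol Table 7, and it should be fixed before unblinding. Agonists and inhaled levodopa are prohibited but named by no label, and one label has no counterpart in Table 7. Between 0 and 5 of the seven groups could be uncaptured; two is the likeliest figure if the list was made for baseline drugs, which is an inference.

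The effect on the treatment estimate is unknown in size and direction, and it is limited to subjects who take an uncaptured drug and stay on study drug. SAP Section 9.6 was not available, so a reader should not infer that the pre-lock identification of cases fails in practice. The conclusion concerns the written rule only.

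**What to change.** Before unblinding:

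- Reconcile the code list in SAP 5.9.1 and in pattern 2b of 5.9.3.3 with the antiparkinsonian items of protocol Table 7, keeping the table's stated exceptions, so that each item is explicitly captured. Dopamine agonists and inhaled levodopa need particular attention.
- Remove ANTICHOLINESTERASES or justify it.
- Point SAP 5.10.1 and 5.11 to the same list and the same 7-day condition.
- As an option, add a sensitivity analysis that sets to missing only those visits whose diary days overlap a course shorter than 7 days.

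This changes which diary data are analysed, not what patients may take. It needs SAP wording and a code list but no new data. The downside is slightly more censoring: about 1.5 points of power (90.4% to 88.9%) under the assumed 5% loss of completers. Made after unblinding, the same edit could look data-driven.

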5.9.2. Main Analytical Approach

The change from baseline to each study visit in total daily "on" time without troublesome dyskinesia based on the 2 day average of the self-completed home diary prior to each visit will be summarized by visit and treatment group. A mixed model repeated measures (MMRM) analysis will be used to analyze the data from all post-randomization timepoints up to Week 27 with fixed effect of treatment group, visits, and interaction between treatment group and visit. The baseline value of total daily "on" time without troublesome dyskinesia (based on the 2 day average prior to the baseline visit) will be included as a covariate. Subject will be included as a random effect. An unstructured covariance structure will be used for the repeated measures. If the unstructured covariance matrix results in convergence issue, the heterogeneous Toeplitz covariance structure followed by the heterogeneous first-order autoregressive (AR(1)) structure will be used. The Kenward-Roger approximation will be used to estimate the denominator degrees of freedom. The difference between tavapadon and placebo at the endpoint visit will be estimated based on the Least Squares Mean (LSMean) difference between the treatment groups at the endpoint visit from the MMRM with the associated 95% confidence interval (CI) and P-value. The missing values are assumed to be missing at random for the main analysis, including missing due to missed visits or early termination due to COVID-19 control measures. Time curve plots will be presented for both raw Mean (SEM) and LSMean (SE).

5.9.3. Sensitivity Analyses

5.9.3.1. Treatment Effect at Final Dose Levels

To assess the treatment effect at the final dose level, a sensitivity analysis will be conducted on the mITT set using the MMRM analysis method described in [Section 5.9.2](#) with treatment defined as the actual final dose level achieved. The final dose level is defined as the dose received at the Week 26 timepoint or at the time of early termination if the subject achieved a minimum of 5 mg prior to discontinuation.

5.9.3.2. Treatment Effect based on Actual Treatment Received

Should a discrepancy between the study treatment received and the randomized treatment assignment occurred in 4 or more subjects, a sensitivity analysis may be conducted based on the study treatments that subjects actually received using the MMRM analysis method described in [Section 5.9.2](#).

5.9.3.3. Impact of Missing Values Handling

Whilst every effort will be made to prevent avoidable missing values during the study conduct ([National Research Council, 2010](#)), it is unrealistic to expect no missing values in clinical trials. The impact of missing values on the analysis results will be assessed by the sensitivity analyses described below.

Under Missing at Random (MAR) Assumption

Multiple imputation (MI) will be performed to replace each missing value with a set of plausible values that represent the uncertainty about the correct value to impute. The Markov chain (MCMC) method will be utilized for the mITT set. SAS PROC MI will be used to generate 27 possible imputed datasets: Each of these datasets will be analyzed using PROC MIXED in SAS using the MMRM model as described in [Section 5.9.2](#). The results of the analyses of the datasets will be combined using PROC MIANALYZE to produce an inferential result.

Considerations of Data Potentially Missing Not at Random (MNAR)

A pattern mixture model (PMM) approach will be used to address potentially MNAR patterns. The following three patterns of subjects in the mITT set will be considered:

- 1) Subjects with no missing values from discontinuation or from initiation of prohibited Parkinson's disease concomitant mediation during treatment period.
- 2) Subjects with missing values from the types of ICEs below will be considered having MNAR
 - a. Subjects who discontinue due to reasons, as recorded on the eCRF, of lack of efficacy, adverse events associated with motor symptoms of Parkinson's disease, physician decision, and withdrawal by subject.
 - b. Subjects who initiated concomitant Parkinson's disease medications (ATC classifications of ADAMANTANE DERIVATIVES, OTHER DOPAMINERGIC AGENTS, OTHER ANTIPARKINSON DRUGS, MONOAMINE OXIDASE B INHIBITORS, or ANTICHOLINESTERASES) after the first dose of IMP and prior to the last dose of IMP with a use duration of 7 days or more will be considered having a potential confounding ICE. The efficacy data post ICE will be treated as missing with the missing pattern of MNAR.

The MNAR cases will be identified and documented prior to database lock and unblinding ([Section 9.6](#)).

- 3) Subjects with missing values from the type of ICEs below will be considered as having MAR
 - a. Missing values after discontinuation due to reasons, as recorded on the eCRF, of death, pregnancy, loss to follow-up, adverse event unrelated to motor symptoms of Parkinson's disease, non-compliance, site termination, protocol deviation, failure to meet continuation criteria and other will be considered as MAR.

The MNAR pattern 2) above in the active treatment group will be imputed using the jump to reference (J2R) method (Cro et. al. 2020) by assuming that patients jump to behave like those in the placebo group following their last observed time point. However, such MNAR in the placebo group will still be imputed as MAR using the standard multiple imputation method.

The MAR patterns 3) will be imputed using the standard multiple imputation method described above.

Other missing values due to missed visits/assessments before endpoint or discontinuation will also be assumed as MAR and imputed using the standard multiple imputation method for all three patterns.

Core codes for MAR and MNAR imputations are provided in [Section 9.7](#).

Under Missing Completely at Random (MCAR) Assumption

An additional sensitivity analysis will be conducted on the Endpoint (Week 26) Completer set using the MMRM analysis method described in [Section 5.9.2](#).

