9.2 Sample Size Determination

A sample size of 184 subjects per group (total, 368 subjects) will provide at least 90% power to detect a change in the primary outcome measure (change from baseline in “on” time without troublesome dyskinesia) of 1 hour with a standard deviation of 2.5, a 2-sided alpha level = 0.049, and assuming a 27% dropout rate.

In the event of higher than anticipated early terminations due to COVID-19 or other reasons, Cerevel may extend enrollment in order to maintain the planned statistical power.

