9.7. Core Codes for imputation of MAR and MNAR

9.7.1. Imputation of Missing at Random (MAR) Cases

SAS PROC MI will be used to generate 27 possible imputed datasets using the following SAS code:

```
proc mi data=mcmc1 seed=SEED1 nimpute=27 out=Out1X;
mcmc chain=multiple displayinit initial=em(itprint);
var TRT y0 y1 y2 ... yn;
run;
```

Here, TRT is an indicator variable representing treatment with values of 'CVL-751' or 'Placebo', Y₁ - Y_N represent the response variable (e.g., 'ON' time without troublesome dyskinesias) for each visit, Y₀ is the baseline score, and SEED1 is a random number.

Each of these datasets will be analyzed using PROC MIXED in SAS using the MMRM model. The results of the analyses of the datasets will be combined using PROC MIANALYZE to produce an inferential result.

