9.7.2. Imputation of Missing Not at Random (MNAR) Cases

The MNAR cases are imputed using reference based imputation (J2R) method. The five macros; SAS code for reference based multiple imputation [<https://www.lshtm.ac.uk/research/centres-projects-groups/missing-data#dia-working-group>] will be used to generate 27 possible imputed datasets using the following sample SAS code:

```
%include "&Path\part1A_33.sas";
%include "&Path\part1B_47.sas";
%include "&Path\part2A_40.sas";
%include "&Path\part2B_31.sas";
%include "&Path\part3_55.sas";
%include "&Path\plotter_7.sas";

%part1a(Jobname=X, Data=XX, Subject=usubjid, Response=aval, Time=avisitn, Treat=Trt01pn, cov=BASE, covgroup=trt01pn, Debug=1);
%part1b(Jobname=X, Ndraws=27, thin=350, seed=s, Debug=1);

%part2a(Jobname=X_J2R, inname=XX, method=J2R, ref=0, Debug=1);
%part2b(Jobname=X_J2R, seed=s, Debug=1);
```

Each of these datasets will be analyzed using PROC MIXED in SAS using the MMRM model. The results of the analyses of the datasets will be combined using PROC MIANALYZE to produce an inferential result.

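### With 27 imputations and no fixed seeds, a borderline p-value from the multiple-imputation or jump-to-reference analysis can change sides of 0.05 on rerun, although the estimate barely moves

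*SAP*

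**What the plan says.** SAP 5.9.3.3 plans three checks on missing data: multiple imputation under missing at random (MAR); a pattern-mixture analysis that applies jump-to-reference to the tavapadon cases classed as missing not at random (MNAR); and a completer analysis. SAP 5.10.3 repeats them for the key secondary endpoint.

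- **MAR imputation.** The text says "SAS PROC MI will be used to generate 27 possible imputed datasets". The code in 9.7.1 reads "proc mi data=mcmc1 seed=SEED1 nimpute=27 out=Out1X", and the only description of the seed is "SEED1 is a random number".
- **Jump-to-reference.** SAP 9.7.2 says that the macros "will be used to generate 27 possible imputed datasets using the following sample SAS code". The two calls that take a seed are "part1b(Jobname=X, Ndraws=27, thin=350, seed=s, Debug=1" and "part2b(Jobname=X_J2R, seed=s, Debug=1".

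The SAP gives no seed value, no reason for choosing 27, and no check on Monte Carlo error.

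The main analysis (SAP 5.9.2) is a mixed model for repeated measures (MMRM) without imputation. Formal testing (SAP 5.4) covers only the primary and key secondary hypotheses.

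**The concern.** A multiple-imputation result carries Monte Carlo error because only a finite number of imputations is drawn. With 27 draws that error is small for the estimate, but it can be large enough to move a borderline p-value across 0.05. Because the seed is not set in advance, the reported number is one draw from that spread, and nothing in the SAP says which draw it must be.

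What is at stake is how the sensitivity results are read. Jump-to-reference is the one planned analysis that departs from MAR in the direction unfavourable to tavapadon. A reader comparing its p-value with that of the main analysis should be seeing the effect of the assumption, with no visible contribution from the seed.

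**Working it through.** **1. Inputs, and the plan's own figure.** Protocol 9.2 assumes "1 hour with a standard deviation of 2.5, a 2-sided alpha level = 0.049, and assuming a 27% dropout rate". SAP Table 5 counts 270 completers, which is 135 per arm.

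SE = 2.5 × √(2/135) = 0.304 h.

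A noncentral t calculation at two-sided 0.049 gives power of 90.4%, as in Table 5. The rows for SD 3.0 (77.6%) and SD 4.0 (53.1%) also reproduce.

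**2. Error in the estimate.** The seed-to-seed SD of the pooled difference is SE × √(FMI/m), where m is the number of imputations. The documents give no FMI, so I assumed 0.05 to 0.27. The upper value is the dropout rate itself, which applies if earlier visits tell nothing about Week 26. At FMI 0.27 and m = 27, √(0.27/27) = 0.10, so the SD is 0.10 × 0.304 = 0.030 h.

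**3. Error in the p-value.** Take a result whose p-value is 0.045 in the limit of many imputations (z = 2.00). For each seed:
- draw the pooled estimate with the SD from step 2;
- draw the between-imputation variance B as a scaled chi-square on m − 1 degrees of freedom;
- form the total variance W + (1 + 1/m)B, with W the within-imputation variance;
- take p from a t distribution with Barnard-Rubin degrees of freedom.

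Results for m = 27:

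| FMI | SD of difference (h) | 95% of seeds give p | Share with p ≥ 0.05 |
|---|---|---|---|
| 0.05 | 0.013 | 0.037–0.057 | 22% |
| 0.10 | 0.019 | 0.034–0.063 | 31% |
| 0.20 | 0.026 | 0.029–0.074 | 40% |
| 0.27 | 0.030 | 0.026–0.082 | 43% |

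The limiting p is taken on the normal scale and the pooled values on the t scale. That alone moves the median to about 0.046 even at m = 1000, so a few percentage points of these shares are not seed noise.

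**4. Width of the sensitive zone.** At FMI 0.27 the chance of landing on the other side of 0.05 is 7% from a limit of 0.03, 0.6% from 0.02, about 0 from 0.01, 9% from 0.07 and 0.3% from 0.10.

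**5. Check on simulated trial data.** I used 184 per arm, five visits, 27% monotone dropout and within-subject correlation of 0.4, 0.6 or 0.8 (assumed), and resampled sets of 27 from 6000 imputations. From a limit of 0.045:
- MAR imputation: FMI 0.09–0.21, with 27–38% of sets at or above 0.05.
- Jump-to-reference: FMI 0.10–0.18, with 29–38% at or above 0.05.

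**6. Larger m.** For FMI 0.10 to 0.27, the share at or above 0.05 from a limit of 0.045 is 15–31% at m = 100, 1–12% at m = 500 and 0–4% at m = 1000. At m = 1000 the SD of the difference is 0.003 to 0.005 h.

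**7. How often it would arise.** Under the design effect of 1 h, the chance that p falls between 0.03 and 0.07 is about 6%. If jump-to-reference diluted the effect to 1 × (1 − 0.27) = 0.73 h, treating every tavapadon dropout as MNAR, it would be about 13%.

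**The case against.** The strongest reply is that nothing decisive rests on these p-values. The MMRM carries the confirmatory tests of both endpoints and needs no seed, and SAP 5.9.3.3 and 5.10.3 attach no threshold to a sensitivity result. The estimate moves by at most about 0.03 h (SD) against a 1 h target, and the zone in which p can cross is narrow. All of that stands, and it limits the point to a cheap improvement.

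The seed can also be defended. SAP 5.9.3.3 presents the 9.7 code as core code, 9.7.2 calls its own code a sample, and file paths and job names are placeholders too. SAP 9.5 requires verification by independent programming, which in practice would need a shared, recorded seed. A reader might infer that the results could not be reproduced, but a recorded seed reproduces them at any m. What remains is that the seed is not set before unblinding; on its own that would be only a missing detail.

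A reader might also infer that these runs are the only evidence on whether the results survive the missing-data assumptions. The documents do not support that, because SAP 5.9.3.3 also plans an MMRM on Week 26 completers, with no imputation. The MAR imputation largely repeats the assumption of the main model. The narrower statement holds: jump-to-reference is the only MNAR check.

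**Conclusion.** The point holds as a minor one. With 27 imputations the pooled difference has a seed-to-seed SD of about 4 to 10% of its standard error. A sensitivity p-value with limit 0.045 would be reported at or above 0.05 for roughly 22 to 43% of seeds. Outside limiting values of about 0.03 to 0.07 the problem fades, and at 0.02 or below, or 0.10 or above, it is practically absent.

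A tenth of the standard error is the top of the range and should not be read as typical; it requires that earlier visits carry no information. It would also be wrong to conclude that the trial's success could turn on a seed, since the primary result and the testing hierarchy do not involve one.

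The figures rest on assumed FMI values and within-subject correlations, on the design SD of 2.5 and 27% dropout, and on 0.05 as the conventional reading line (the primary test itself uses 0.049).

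**What to change.** Replace 27 by 1000 (at least 500) in all five places: the prose of SAP 5.9.3.3, 9.7.1 and 9.7.2, nimpute in the PROC MI call, and Ndraws in part1b. Changing only the code would leave the text contradicting it. In the same revision, before unblinding, write fixed integer seeds for PROC MI, part1b and part2b.

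The two changes do different work: the fixed seed makes the result reproducible, and the larger number of imputations reduces the error. No new data, visits or design changes are needed. The only downside is longer run time.
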